shoulder arthroscopy who receive post-operative CBD and a placebo group. Patients will be asked on postoperative Day 1, 2, 7, and 14 to rate their pain according to the VAS scale. Additionally, opioid consumption, CBD consumption, as well as patient satisfaction will be measured. Patients will be asked in the post-trial period to fill out a questionnaire pertaining to 1-year outcomes. The questionnaire will be in the form of a single online survey including ASES score, VAS score, KJOC Shoulder score, and SANE score.

Rationale for multi-center study:

The second site is essential for this project, for both recruitment and logistical purposes. While NYULOH does have high-volume, a large proportion of these patients will be ineligible due to the exclusion criteria and will not want to participate given that this is a randomized, controlled, double blinded study. Additionally, the second site PI was absolutely instrumental in the conceptualization and the design of this study, as well as securing the necessary funding for it happen. This study would not be feasible without their collaboration. Additionally, the second site PI has an academic appointment here at NYU Langone, and is instrumental in the education of the trainees here at our institution

Primary Objective

The primary objective of the study is to determine if there are any differences in post-operative pain between patients receiving CBD after shoulder arthroscopy compared to patients who do not receive it.

Secondary Objective

Secondary objective of the study is to determine if there are any differences in patient satisfaction, the incidence of opioid induced nausea, and the numbers of opioids and CBD/placebo ODTs consumed by the two patient cohorts.

II. CHARACTERISTICS OF THE RESEARCH POPULATION

Number of Subjects

We will aim to enroll a total of 100 subjects (50 per cohort) as determined by the priori sample size calculator.

Gender of Subjects

Men and women will be included in this study.

Age of Subjects

Subjects included study will be aged 18-75 years, inclusive.

Racial and Ethnic Origin

There are no enrollment restrictions based on race or ethnic origin.

Inclusion Criteria

Patients will be screened for eligibility using the following criteria. All study subjects must meet the following inclusion criteria:

- Patients undergoing an arthroscopic shoulder procedure (rotator cuff repair, decompression, labrum repair)
- Patients ages 18-75, inclusive

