Information to be recorded pre-operatively includes age, sex, height, weight, BMI, and American Society of Anesthesiology (ASA) classification. As well as baseline levels of complete blood count (CBC), chemistry profile, liver enzymes, gamma glutamate transferase (GGT), electrocardiogram, urine analysis, 12-panel urine drug test, and a urine pregnancy test.

Intra-operative information will also be recorded, including operative time, procedure, number of anchors, and complications. Patients will subsequently be stratified in different subgroups based on the procedure performed.

Pain severity scores at rest will be assessed by use of a visual analog scale (VAS; 0 = no pain, 10 = worst pain imaginable) at 6, 24, and 48 hours as well as 7 days and 14 days after surgery.

Patients will record their satisfaction with their management, on a 0-10 scale, 24 hours, 2 days and 7 days, and 14 days after surgery.

Additionally, any nausea experienced by the patients will be recorded by use of a VAS (0 = no nausea, 10 = worst nausea imaginable) at 2 days, 7 days and 14 days after surgery.

Percocet consumption will be recorded at 24 hours, 2 days and 7 days, and 14 days after surgery. Additionally, subjects will be asked to record the dates and times of CBD consumption.

Liver function tests, consisting of the standard hepatic panel, and including serum transaminase and bilirubin levels will be administered for study purposes on Day 7 and Day 14 after surgery.

Incidence of CBD-related side effects will be noted. Time to discharge from the post-anesthesia care unit (PACU) and time to discharge from the hospital will be recorded. Patients will be in the study a duration of 14 days and will be asked to fill out one online survey at the 1-year mark to determine the long-term effects that may be associated with using CBD.

In order to maintain the blinding, all data, including pain severity scores, side effects, opioid and CBD consumption, will be collected by the resident physician or physician assistant. However, if needed, in the event of an emergency or SAE, the unblinded surgeon responsible for randomization will be able to confirm whether a subject has been assigned to receive CBD or placebo.

| Study Time Points | |
|------------------------|---|

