| Day 0 - Day of Surgery | Baseline suicidality assessment (C-SSRS), Record Pain (6hrs and 24 hrs), Record clinical data during surgery and post op including time to discharge from PACU and time to discharge from the hospital, monitor for AEs |
| Day 1 | Record Pain, Opioid consumption, CBD consumption, Satisfaction, monitor for AEs |

The use of cannabidiol (CBD) in pain reduction and opioid use after shoulder arthroscopy. A Double-Blind, Randomized Control Study

Version 06/28/2022

| | |
|-----------------------------------|--|
| Day 2 | Record Pain, Opioid consumption, CBD consumption, Satisfaction, Nausea, monitor for AEs |
| Day 7 - Standard of Care Visit 1 | Record Pain, Opioid consumption, CBD consumption, Satisfaction, Nausea, Liver Function Tests - Non-standard of care, C-SSRS, Drug accountability, monitor for AEs |
| Day 14 - Standard of Care Visit 2 | Record Pain, Opioid consumption, CBD consumption, Satisfaction, Nausea, monitor for AEs Liver Function Tests - Non-standard of care, C-SSRS, Drug accountability and review of completed subject diary, monitor for AEs |
| Month 12 – Post-Trial Survey | Record Pain; Complete ASES, KJOC Shoulder, and SANE assessment |

Data Analysis and Statistical Plan

Our power analysis was based on the literature of post-operative pain control following shoulder arthroscopy. Under the assumption of a VAS of 3 and 1.8 for the control and CBD respectively, with a SD of 2: Group sample sizes of 45 in each group would achieve 80% power to reject the null hypothesis of equal means when the population mean difference between Control and CBD is $\mu_1 - \mu_2 = 3.0 - 1.8 = 1.2$ with a standard deviation for both groups of 2.0 at a significance level (alpha) of 0.05 using a two-sided two-sample equal-variance t-test. Thus, to allow for a 5% drop-out at 14-day follow-up, 100 patients would be required to enroll.

For descriptive statistics, categorical values will be described by percentages, and continuous variables will be described by means with standard deviations. To compare primary and secondary outcomes, a T-Test will be performed, with a p-value of 0.05 set to determine statistical significance. Testing will be performed to determine whether sample distribution is normal; if not, non-parametric testing will be performed.

Analysis of the Primary Efficacy Endpoint(s)

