To compare primary outcomes (VAS score), a T-Test test will be performed, with a p-value of 0.05 set to determine statistical significance. Testing will be performed to determine whether sample distribution is normal; if not, non-parametric testing will be performed. Patients who do not complete at least 80% of follow-up visits will be considered lost to follow-up and will not be included in the analysis.

Analysis of the Secondary Endpoint(s)

To compare secondary outcomes (opioid use, satisfaction), complication rates), a T-Test will be performed, with a p-value of 0.05 set to determine statistical significance. For categorical variables, a Fisher's exact test will be performed. Testing will be performed to determine whether sample distribution is normal; if not, non-parametric testing will be performed. Patients who do not complete at least 80% of follow-up visits will be considered lost to follow-up and will not be included in the analysis.

Data and Safety Monitoring Plan

Data monitoring will be done by [name], the principal investigator will oversee the conduct of the study. He will review enrollment, accumulated study data, including pain VAS scores, Percocet consumption VAS scores, liver function test results, adverse events, protocol deviations, study compliance and data accuracy quarterly.

He will monitor whether or not:

1. Collection and storage of patient data was performed in a sensitive and secure manner, as defined in the informed consent form and protocol, ensuring information is stored on REDCap.
2. All study activities were conducted with primary emphasis on patient care and wellbeing, ensuring the patients are not in discomfort and have an abnormally high VAS following the surgery.
3. If there were any adverse events, and if so were addressed appropriately and per protocol
4. The risk/benefit to patients has remained the same throughout the course of the study.

The study will be stopped if there are unexpected severe adverse events in more than one patient. Adverse Events (AEs) will be defined as negative reactions to the CBD treatment. We will submit summaries of data and safety monitoring to the IRB annually. De-identified primary and secondary outcome data will be shared by the participating site PI quarterly, and they will notify the host site PI ([name]) upon each enrolled patient.

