Any study event that is:

- associated with the use of the study device, and
- unanticipated,
- regardless of the seriousness of the event.

- ***Within 5 working days (via written report)***

- Protocol deviation to protect the life of the subject in emergency
- Withdrawal of IRB approval
- Lack of informed consent

Additional reporting requirements

The sponsor-investigator is also required to identify in IND safety reports all previous reports concerning similar adverse events and to analyze the significance of the current event in light of the previous reports.

Reporting Process

Adverse events may be submitted on FDA Form 3500A (MEDWATCH Form) or in a narrative format meeting FDA requirements. The contact information for submitting IND safety reports is noted below: [name],

The use of cannabidiol (CBD) in pain reduction and opioid use after shoulder arthroscopy. A Double-Blind, Randomized Control Study

Version 06/28/2022

Division of Anesthesiology, Addiction Medicine, and Pain Medicine (DAAP)
[name]
[contact]
[contact]

Notifying participating sites: The study PI will notify the participating sites within 24 hours.

IV. RISK/BENEFIT ASSESSMENT

Risk

This study involves risk of medication side effects as well as a breach of confidentiality. Oral CBD can cause the following side effects:

- Fatigue
- Diarrhea
- Changes in appetite/weight

Rare side effects include:

- Unusual tiredness or weakness
- Hepatic toxicity
- Testicular toxicity was observed in a preclinical study where mice were given CBD, although this has not been observed in clinical studies.

Protection against Risks

Patients will be screened for any contraindication to CBD or Percocet use, including Cannabis dependence. Patients will receive baseline assessments for history and physical, including psychiatric exam, complete blood count (CBC), chemistry profile, liver enzymes, gamma glutamate transferase (GGT), electrocardiogram, urine analysis, 12-panel urine drug test, and urine pregnancy test.

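### No pre-operative pain VAS is recorded for a trial whose primary outcome is pain VAS, so baseline pain can be neither adjusted for nor displayed; this is a cheap efficiency gain forgone, not an error

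*Combined protocol and SAP*

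**What the plan says.** The pre-operative data are listed in Methods and Procedures: "Information to be recorded pre-operatively includes age, sex, height, weight, BMI, and American Society of Anesthesiology (ASA) classification", followed by blood tests, ECG, urine analysis, drug screen and pregnancy test. Protection against Risks gives a matching baseline list: "Patients will receive baseline assessments for history and physical, including psychiatric exam, complete blood count (CBC), chemistry profile, liver enzymes" and further tests. Neither list contains a pain score.

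Every pain assessment comes after surgery:

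- Study Design: "Patients will be asked on postoperative Day 1, 2, 7, and 14 to rate their pain according to the VAS scale".
- Methods and Procedures: VAS at rest "at 6, 24, and 48 hours as well as 7 days and 14 days after surgery".
- Study Time Points, Day 0 row: "Record Pain (6hrs and 24 hrs" post-operatively, although the same row includes a baseline C-SSRS.
- Study Time Points, Month 12 row: pain is recorded in the post-trial survey.

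The section on the primary efficacy endpoint says: "To compare primary outcomes (VAS score), a T-Test test will be performed, with a p-value of 0.05 set to determine statistical significance". A non-parametric test is substituted if the data are not normal. No covariate is planned anywhere, and no correlation between pre-operative and post-operative pain is stated.

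**The concern.** Patients differ in how much pain they bring to surgery and in how they score it. When the outcome is a self-reported pain scale, a pre-operative score on that scale is the natural covariate for removing some of this between-patient variation from the error term. Here it is not collected, so the variation stays in.

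The second loss is descriptive. Eligible procedures are mixed (rotator cuff repair, decompression, labrum repair), and block randomisation is described without a stated stratification factor. A reader of the results will want to see that the arms began with similar pain, and the data for that table will not exist.

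Patients already have a pre-operative contact with blood tests, ECG, urine tests and a suicidality assessment, so the score could be obtained at almost no cost.

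**Working it through.** **Inputs from Data Analysis and Statistical Plan.** Means 3.0 and 1.8 (difference 1.2), SD 2.0 in both arms, two-sided alpha 0.05, 45 per arm, 80% power, 5% drop-out, 100 enrolled.

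**Input that is assumed.** r, the correlation between pre-operative and post-operative VAS. The documents give none, so a range of 0 to 0.5 is shown.

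**Step 1: the plan's own figure.** Standard error of the difference = 2.0 × √(2/45) = 0.422. Noncentrality = 1.2 / 0.422 = 2.85 on 88 degrees of freedom. Noncentral-t power = 80.4%. At 44 per arm it is 79.5%, so 45 is the smallest sufficient number. The stated figure reproduces.

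**Step 2: what the enrolment target leaves.** 100 × 0.95 = 95 evaluable, or 47.5 per arm. Unadjusted power there is 82.5%.

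**Step 3: adjustment with a baseline score for everyone.** Residual variance = 4 × (1 − r²), with one further degree of freedom used.

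**Step 4: adjustment with a baseline score for half the patients (assumed share).** Missing baselines are set to the overall mean and flagged by an indicator. The variance falls only among those with a score, so the average residual variance is about 4 × (1 − r²/2). Two further degrees of freedom are used.

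| Assumed r | Residual SD, all collected | Power at 45 per arm, all collected | Power at 45 per arm, half collected |
|---|---|---|---|
| 0 | 2.00 | 80.4% | 80.3% |
| 0.1 | 1.99 | 80.7% | 80.5% |
| 0.2 | 1.96 | 81.9% | 81.1% |
| 0.3 | 1.91 | 83.9% | 82.1% |
| 0.4 | 1.83 | 86.7% | 83.5% |
| 0.5 | 1.73 | 90.1% | 85.3% |

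With full collection, the half-width of the 95% confidence interval at 45 per arm falls from 0.84 to 0.82 at r = 0.2, 0.80 at r = 0.3 and 0.73 at r = 0.5.

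**Step 5: the analysis has to change too.** Collecting the score and keeping the unadjusted t-test leaves power at 80.4%. Testing change from baseline is not a substitute. With equal SDs the change score has variance 2 × 4 × (1 − r), which exceeds 4 whenever r is below 0.5.

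**Step 6: the cost if baseline pain predicts nothing.** At r = 0 with full collection, expected power moves from 80.37% to 80.36%.

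**The case against.** The strongest reply is that nothing here is broken. Randomisation makes the unadjusted comparison valid, the power statement assumes no baseline score and is correct, and chance imbalance in pre-operative pain is already allowed for in the t-test's error rate. All of that stands. A reader might infer from the missing baseline that the treatment estimate is biased or the sample size wrong; the documents support neither.

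A reader might also infer that the trial has no precision to spare. The enrolment target says otherwise: 5% drop-out from 100 leaves 82.5% power, a margin as large as the whole gain at r = 0.2. Higher drop-out, or the exclusion of patients who complete fewer than 80% of visits, could use that margin up, but it exists on the plan's own figures.

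The gain may also be small. All patients receive an interscalene block and may take opioid as needed, so early scores could relate only weakly to pre-operative pain. That too is an assumption, and it need not carry over to Days 7 and 14, but it is why the range must start at zero.

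The Month 12 score adds little to the argument, since no change-from-baseline analysis of it is planned.

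Finally, the pre-operative list is introduced as what the data include, so it is not strictly exhaustive. But the design description, the schedule and the baseline safety list do not fill the gap.

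**Conclusion.** The omission is confirmed: no section provides a pre-operative pain score, and the planned comparison uses no covariate. The consequence is lost efficiency and a baseline comparison that cannot be shown.

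The gain forgone ranges from nothing at r = 0 to about 10 percentage points of power at r = 0.5 with full collection, and to about 5 points if only half the patients have the score. These figures take the plan's difference of 1.2, SD of 2.0 and 45 per arm as given. They rest on an assumed r, which may differ between time points, and on an assumed share of patients with a baseline, since the documents do not state enrolment to date. The upper figure should not be read as what the trial would achieve.

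It is worth doing because the expected loss is negligible even if baseline pain turns out to be uninformative.

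**What to change.** 1. Add pain VAS at rest (0-10) to the pre-operative list in Methods and Procedures, and to the Day 0 row of Study Time Points as a pre-surgery item.
2. In Data Analysis and Statistical Plan and in the primary endpoint section, replace the t-test on VAS with a linear model of VAS on treatment and baseline VAS. Do not use change scores.
3. State which time points are modelled. The plan lists 6, 24 and 48 hours and Days 7 and 14 without naming one as primary, so the model needs to be specified for each time point analysed.
4. Replace the switch to a non-parametric test with a rank-based or robust version of the same model, reported as a sensitivity analysis if the residuals are non-normal.
5. For patients enrolled before the change, set baseline to the overall mean and include a missing indicator. Covariate and indicator together use up to two degrees of freedom.
6. Fix all of this in writing before unblinding, and report baseline VAS by arm with the number observed.

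The cost is one question at an existing contact, one or two model terms and an amendment. The gain is small if r is 0.2 or less, and partial in any case because patients already enrolled have no baseline value.

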Patients indicated and scheduled for a shoulder arthroscopy will be identified from faculty surgeon case logs at the NYU Langone Health, Langone Orthopedic Hospital Sports Medicine Division. After informed consent is obtained, a chart review of patients' medications and past medical histories will be performed based on their electronic medical records to identify any current pain medications or exclusion criteria. In order to maintain the blind, another surgeon not involved in the procedure will randomize the patient to one of two cohorts using REDCap. Both surgeons are members of the study team. The randomization will be block randomization, via a computer generator on RedCap.

- Cohort 1: CBD ODTs to be administered with routine post-operative pain management regimen
- Cohort 2: Will not receive CBD; but a visually indistinguishable placebo ODT instead.

The resident physician, physician assistant, anesthesiologist, surgeon and study team members will remain blinded. Additionally, all patients will receive a traditional upper extremity interscalene block as per routine.

Immediate post-operative management will not be affected by this study. All patients will receive a standardized regimen of Percocet for pain management, which is standard of care post-operative treatment. Patients will receive a standard dose of 5/325mg and be discharged with 30 tabs and will be instructed to take 1-2 tablets, as needed, every 4-6 hours.

Additionally, patients will be randomized into one of two cohorts. The first cohort will receive a 25mg CBD ODT, every 4-6 hours as needed, with instructions to take two CBD ODTs if they weigh more than 80 kg (total maximum of 50mg per dose every 4-6 hours as needed). Cohort 2 will receive the same instructions, but with the placebo ODT instead. The dose of 25mg for subjects weighing \geq 80kg and 50mg for subjects weighing more than 80kg was selected based on recommendations from the FDA.

The use of cannabidiol (CBD) in pain reduction and opioid use after shoulder arthroscopy. A Double-Blind, Randomized Control Study

Version 06/28/2022

All subjects will be required to refrain from use of THC, or other cannabis-related products for the duration of the study.

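### Procedure is recorded and earmarked for subgroups but left out of the primary pain comparison: a modest loss of precision, and subgroups with no stated purpose that are too small to test separately

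*Combined protocol and SAP*

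**What the plan says.** Under Inclusion Criteria, three kinds of operation qualify: "Patients undergoing an arthroscopic shoulder procedure (rotator cuff repair, decompression, labrum repair").

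Section III, Methods and Procedures, describes allocation in one sentence: "The randomization will be block randomization, via a computer generator on RedCap". It names no stratification factor and no block size, although the trial has two sites. The same section records procedure and number of anchors among the intra-operative data and continues: "Patients will subsequently be stratified in different subgroups based on the procedure performed". It does not say what those subgroups are for.

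The Data Analysis and Statistical Plan treats all operations as one population: "Under the assumption of a VAS of 3 and 1.8 for the control and CBD respectively, with a SD of 2". Under Analysis of the Primary Efficacy Endpoint(s), VAS is compared by a t-test, or a non-parametric test if the data are not normal. There is no term for procedure or site. No subgroup hypothesis, interaction test or multiplicity rule appears.

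**The concern.** The plan treats procedure as important enough to divide patients by, yet does not use it where it could help: in the allocation as described, or in the primary comparison. If the three operations differ in expected pain, the between-procedure spread stays in the error term of the t-test and the treatment effect is estimated less precisely than the same data allow.

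The second issue is the split itself. With no stated purpose, it leaves room for a separate p-value in each operation. Groups that small would usually miss the planned effect, and a mixture of significant and non-significant results could be read as the drug working after one operation and not another.

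**Working it through.** **Inputs.** From the Data Analysis and Statistical Plan: difference 3.0 − 1.8 = 1.2, SD 2.0, two-sided alpha 0.05, 45 evaluable per arm. From Number of Subjects: 100 enrolled, 50 per arm. The documents give neither the procedure mix nor pain by procedure, so those inputs are assumptions and are marked as such.

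**1. The plan's own figure.** The protocol says "Group sample sizes of 45 in each group would achieve 80% power". For a two-sample t-test the noncentrality is 1.2 / (2.0 × √(2/45)) = 1.2 / 0.4216 = 2.85 on 88 degrees of freedom. Power is 80.4% at 45 per arm and 79.5% at 44, so the stated figure is reproduced.

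**2. Does chance imbalance damage the primary test?** Assume one procedure makes up a third of 90 patients (30 of 90). Under 1:1 allocation without strata:
- SD of its count in one arm = √(45 × 1/3 × 2/3 × 45/89) = 2.25.
- SD of the between-arm difference in share = 2 × 2.25 / 45 = 0.10, or 10 percentage points. A difference of at least 10 points has probability 26%; at least 20 points, 4%.
- If that procedure differs from the others by 1 VAS point (assumed), the shift in the contrast has SD 0.10; if by 2 points, 0.20.

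The yardstick is the standard error of 0.42, which already contains this variation. A simulation of 10,000 trials per scenario (90 patients, unstratified blocks of 4, three equally common procedures with means spanning 2 points, total SD 2.0) gave the unadjusted t-test a type I error of 5.1%, a mean estimated effect of 1.20 and power of 80%. Adjusting for procedure gave 86% power.

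**3. What adjustment gains.** If procedure explains a share R² of VAS variance, the residual SD is 2.0 × √(1 − R²). At 45 per arm:

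| R² (assumed) | Residual SD | Power |
|---|---|---|
| 0 | 2.000 | 80.4% |
| 0.05 | 1.949 | 82.3% |
| 0.10 | 1.897 | 84.3% |
| 0.15 | 1.844 | 86.3% |

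To give R² a scale: with one procedure at a third of patients differing by Δ from the rest, R² = (1/3 × 2/3 × Δ²) / 4 = Δ²/18. So 5-15% corresponds to Δ = √0.9 to √2.7, about 0.9 to 1.6 VAS points. Spending three degrees of freedom on two procedure terms and one site term changes these powers by less than 0.1 percentage point.

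The table assumes that the SD of 2.0 already includes between-procedure spread. If it is a within-procedure SD instead, then for three equally common, evenly spaced procedures the unadjusted power is 79% (means spanning 1 point) or 74% (spanning 2 points).

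**4. If the subgroups were tested separately.** Equal thirds of 90 give 15 per arm (assumed mix):
- Power for 1.2 points with SD 2.0 is 35%.
- 95% CI half-width = 2.048 × 2.0 × √(2/15) = 1.50 points, wider than the planned effect.
- Three independent tests at 0.05 give 1 − 0.95³ = 14.3% chance of at least one false positive.
- The difference in effect between two such subgroups has standard error 2.0 × √(4/15) = 1.03, so power for a 1.2-point difference is about 21%.

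An assumed 60/20/20 mix gives 58% power in the largest group (27 per arm) and 22% in each smaller one (9 per arm). Giving each of three equal subgroups 80% power would need 3 × 90 = 270 evaluable patients.

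**The case against.** The strongest reply is that block randomisation without strata, followed by an unadjusted t-test, is a valid design. That stands. A reader might infer from the pooling of three operations that the primary pain contrast is biased or its error rate inflated. The documents do not support this: allocation is random, imbalance is random error, and step 2 shows the nominal error rate and an unbiased estimate. Nor does subgrouping by the procedure performed introduce treatment-related bias, since the study tablets are given after surgery.

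A reader might also infer that the sponsor intends a significance test within each operation. No such test is announced, and the sentence on subgroups is compatible with descriptive reporting. The 35% figure is therefore conditional on a use that the plan leaves open but does not state.

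Three further points hold in part. The absence of strata is read from silence; the REDCap set-up may contain them, in which case the protocol should say so. The pain gap between operations is assumed, and the interscalene block and common Percocet regimen may narrow it, at least early. The gain from adjustment is also similar to what the enrolment margin already offers: "We will aim to enroll a total of 100 subjects (50 per cohort") gives 84% power if all are evaluable. But adjustment needs no patients, and the two gains add. None of these points supplies the missing purpose for the subgroups or a reason to leave procedure out of the model.

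**Conclusion.** The concern holds as a cheap improvement, not as a flaw that threatens validity. The plan singles out procedure and then leaves it out of the primary comparison. The cost is a modest loss of precision: about 2 to 6 percentage points of power at 45 per arm, if procedure explains 5-15% of VAS variance and the SD of 2.0 already includes between-procedure spread. If procedure explains almost nothing, the gain is close to nil, but so is the cost of adjusting. No figure is offered for site, because the documents give nothing from which to derive one.

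The subgroup point needs no assumption about pain by procedure, only about mix: with 90 evaluable patients divided among three operations, separate comparisons would be badly underpowered for 1.2 points unless nearly all patients had the same operation.

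**What to change.** Under Analysis of the Primary Efficacy Endpoint(s), replace the unadjusted t-test with one pooled linear model of VAS on treatment, adjusted for procedure and site. Define the procedure categories in advance, including one for combined operations, since the protocol does not say that the three are mutually exclusive. State also what happens to the adjustment if the non-parametric fallback is invoked; otherwise it would be lost at that step.

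In section III, say that procedure subgroups are descriptive, reported with a treatment-by-procedure interaction estimate and confidence interval, and without separate significance claims.

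For patients not yet randomised, stratifying the REDCap blocks by site or by planned procedure is optional. Using both gives 2 × 3 = 6 strata, about 17 patients each if 100 were spread evenly, so some blocks would stay incomplete, and the planned operation may differ from the one performed. Adjustment alone obtains most of the benefit and also covers patients already randomised.

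The cost is two sentences, fixed before unblinding, and a few degrees of freedom. Sparse procedure categories may need merging, so the merging rule should be written at the same time.

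### Does enrolling 100 patients follow from 45 per group and a 5% drop-out allowance?

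*Combined protocol and SAP*

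**What the plan says.** The sample-size paragraph (section III, Data Analysis and Statistical Plan) gives all its inputs. The means and spread are set out as "Under the assumption of a VAS of 3 and 1.8 for the control and CBD respectively, with a SD of 2". The test is specified "at a significance level (alpha) of 0.05 using a two-sided two-sample equal-variance t-test". The result is that "Group sample sizes of 45 in each group would achieve 80% power". The next sentence moves from evaluable to enrolled patients: "Thus, to allow for a 5% drop-out at 14-day follow-up, 100 patients would be required to enroll".

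Section II, Number of Subjects, repeats the total: "We will aim to enroll a total of 100 subjects (50 per cohort) as determined by the priori sample size calculator".

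Neither place mentions rounding up, a reserve, a block-size constraint or an adjustment for a non-parametric test.

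**The concern.** Both sentences present 100 as the output of a calculation, yet the stated inputs give 95 or 96. A reader who checks the paragraph finds that its last step fails and cannot tell why. The percentage could be a slip for 10%, since 90/0.90 is exactly 100, or 48 per group could have been rounded to 50 without comment. The two readings imply different planned loss rates.

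Had the error run the other way, with enrolment too small for the stated loss, the trial would have been planned below its own power target. That possibility is why the step deserves a check.

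**Working it through.** **Inputs** (all from the sample-size paragraph, except the 1:1 split, which is in Number of Subjects): difference 3.0 − 1.8 = 1.2; SD 2.0 in both groups; two-sided alpha 0.05; equal-variance t-test; 45 per group; 5% drop-out at 14 days; 100 enrolled, 50 per group.

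**Step 1: the plan's own figure, 45 per group.** Power comes from the noncentral t distribution with n1 + n2 − 2 degrees of freedom and noncentrality

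δ / (SD × √(1/n1 + 1/n2)).

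At 45/45 this is 1.2 / (2 × √(2/45)) = 1.2 / 0.4216 = 2.85 on 88 degrees of freedom, and power is 80.4%. At 44/44 power is 79.5%. So 45 is the correct minimum for 80%, and the plan's figure reproduces.

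**Step 2: from evaluable to enrolled at 5% loss.**

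| Method | Calculation | Enrolment |
|---|---|---|
| Divide the total by the retained fraction | 90 / 0.95 = 94.7 | 95 |
| Divide each group by the retained fraction | 45 / 0.95 = 47.4, so 48 | 96 |
| Multiply the total by 1.05 | 90 × 1.05 = 94.5 | 95 |
| Multiply each group by 1.05 | 45 × 1.05 = 47.25, so 48 | 96 |

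None of these gives 100. The surplus is 4 patients over 96, or 5 over 95.

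**Step 3: what could give 100.** The list is open-ended, and the documents state none of these:

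- Rounding 48 per group up to 50.
- A 10% allowance: 90 / 0.90 = 100.
- Reading 5% as 5 patients per group: 45 + 5 = 50.
- An allowance for the rank test that the plan holds in reserve. With the usual large-sample efficiency under normality of 3/π = 0.955 (an assumption, not in the documents), 45 / 0.955 = 47.1 and 47.1 / 0.95 = 49.6, so 50 per group.
- Filling whole randomisation blocks. Block sizes are not given; with blocks of 10, 94.7 rounds up to 100.

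**Step 4: what 100 delivers.**

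| Enrolled | Loss | Evaluable (n1/n2) | Power |
|---|---|---|---|
| 96 | 5% (96 × 0.95 = 91.2) | 45/46 | 80.8% |
| 100 | none | 50/50 | 84.4% |
| 100 | 5%, balanced | 47/48 | 82.5% |
| 100 | 5%, all in one arm | 45/50 | 82.4% |
| 100 | 10%, balanced | 45/45 | 80.4% |
| 100 | 10%, all in one arm | 40/50 | 79.9% |

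Under the stated 5% loss, 100 meets the power target however the losses fall. The only entry below 80% needs twice the stated loss, all of it in one arm, and even then the shortfall is 0.1 percentage points.

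**The case for a change.** The strongest case for a correction is that rounding up is legitimate but should be disclosed, and that the wording here leaves no room for it because 100 is called the required number and attributed to the calculator. A correction would cost one sentence and one clause. That much stands: the published statement cannot be reproduced from its own inputs, and the basis for 100 is not given.

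A second argument is that the drop-out percentage must match enrolment because the analysis omits incomplete patients: under Analysis of the Primary Efficacy Endpoint(s), those who complete fewer than 80% of follow-up visits "will be considered lost to follow-up and will not be included in the analysis". This does not stand as support. The 5% is drop-out at 14 days, whereas the exclusion rule counts visits. If the visits are Days 1, 2, 7 and 14, a patient who misses one has completed 3/4 = 75% and is excluded even if seen on Day 14. The removals for raised liver tests under Subject withdrawal criteria are a further source of loss. Actual loss could therefore exceed 5%. That would be a reason to welcome the surplus; it does not make the enrolment figure wrong.

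Nor is there a neutral replacement text. Declaring 96 the calculated number would be false if the sponsor had used 10% or a rank-test adjustment, and changing 5% to 10% would be false if 48 had simply been rounded up.

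**Conclusion.** The arithmetic point is correct: 45 per group and 5% drop-out give 95 patients, or 96 with equal arms, and the step to 100 is unexplained. It does not call for a change to the plan. The gap is 4 to 5 patients in the safe direction. At the stated loss power is about 82.5% against a target of 80%, and the target still holds at 10% loss if the losses are balanced.

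A sponsor who follows the plan as written enrols 100, retains enough patients and runs the same test at the same significance level. Any correction would keep all of that, so nothing the trial does or concludes would differ. An analyst writing up the study can report 45 per group as the calculated evaluable number and 100 as the enrolment target without ambiguity.

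This rests on the plan's own difference of 1.2 and SD of 2, and on loss staying at or below about 10%. It does not judge whether the exclusion rule based on visits keeps loss within that bound, which is a separate question from this calculation.
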